8.5. Stopping Criteria

Subjects may be discontinued from study medication and withdrawn from the study if they meet any of the following stopping criteria:

- Any moderate or severe AE that is at least probably related to study treatment and that poses a significant safety risk to the subject, in the opinion of any one of the following: the principal investigator, Amicus Medical Monitor, or SSC
- A serious adverse event (SAE) that is deemed by the investigator or Amicus Medical Monitor to be at least probably related to study treatment
- Intolerable AE, in the opinion of the investigator

Subjects must discontinue study medication and be withdrawn from the study if they meet any of the following stopping criteria:

- Anaphylactic reaction to study treatment, as defined by the Sampson Criteria ([Appendix 1](#))
- SSC decision based on safety data review
- Any of the following abnormal liver function tests in the absence of a reason other than study treatment, to explain the abnormalities
 - Alanine aminotransferase (ALT) or aspartate aminotransferase (AST) $> 8 \times$ upper limit of normal (ULN)
 - ALT or AST $> 5 \times$ ULN for more than 2 weeks
 - ALT or AST $> 3 \times$ ULN and (total bilirubin $> 2 \times$ ULN)

- ALT or AST $> 3 \times$ ULN with the appearance of fatigue, nausea, vomiting, right upper quadrant pain or tenderness, fever, rash, and/or eosinophilia ($> 5\%$)
- Pregnancy

Adverse events that meet the stopping criteria and are reported as serious or severe (per the intensity scale used in Section 11.3), will also be graded using the version of the Common Terminology Criteria for Adverse Events (CTCAE) that is current at study initiation.

Adverse events that meet the stopping criteria will be considered stopping events if they are:

- Deemed related to study treatment
- Classified as Grade ≥ 3 based on the current version of the CTCAE
- In any of the following System Organ Classes:
 - Hepatobiliary Disorders
 - Injury, Poisoning and Procedural Complications
 - Blood and Lymphatic System Disorders
 - Cardiac Disorders
 - Renal and Urinary Disorders
 - Nervous System Disorders

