10.6. Home Infusion

Subjects participating in the study will be considered eligible for administration of ATB200/AT2221 on location at their home or residence after having received ATB200/AT2221 administrations in the study for a period of at least 6 months and not having experienced an IAR for a period of 6 months prior to last infusion. Subjects with history of severe IARs are not eligible for home infusions; subjects with a history including a life-threatening IAR are not eligible for home infusions. Eligible subjects may request participation in the Home Infusion Program with requests granted on a case-by-case basis following discussion between the Medical Monitor and PI with prior approvals granted by Institutional Review Boards (IRBs)/Ethics Committees (ECs), and Regulatory Authorities (RAs). Administration of ATB200/AT2221 will be performed at home for eligible subjects by a trained research home infusion nurse provided by an Amicus designated service provider. All subjects participating in the Home Infusion Program, will be required to complete all functional assessments at their primary site as defined in the protocol. Safety monitoring at home including reporting of AEs, SAEs, and IARs is performed by home infusion nurse. Refer to Section 11.1.3 for further information on IARs, including their reporting and management. The home infusion nurse will document and report the findings direct to sites after every infusion as detailed in the manual for home infusion.

Pre-requisites Criteria:

Inclusion Criteria:

- Received ATB200/AT2221 treatment for a minimum of one year
- Meets following requirements regarding feasibility of the home site for ERT infusion:
 - Availability of utilities and equipment required for storage of Drug Product upon receipt
 - Accessibility for delivery of Drug Product and associated supplies
 - Accessibility of trained home infusion nurse for preparation/administration
 - Preparation of ATB200 lyophilized drug product for reconstitution
 - Infusion of large volume parenteral product
 - Disposal of waste and discarding of used medical supplies
- Amicus/designee deems the home site to be appropriate for home infusion following home assessment
- PI agrees to collaborate with the home infusion agency/home infusion nurse with respect to providing advice and support as needed by the home infusion nurse

Exclusion Criteria:

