Note: The list of IAR symptoms provided in [Table 19](#) is not comprehensive. It is meant to serve as a guideline to the investigators to report and manage IAR as AE. [Table 19](#) also provides a guideline for management of IARs and anaphylaxis (see also [Appendix 1](#)). It is at the investigator's discretion to follow the guidelines or implement treatment protocol that their center is accustomed to following.

In the event that a subject experiences an IAR, the subject should be premedicated for subsequent infusions with antihistamines, steroids, and/or acetaminophen. The premedications should be continued for a period of up to 1 year. Decision regarding discontinuation of premedications should occur only after discussion with Amicus Medical Monitor.

Table 19: Guidelines for Management of Immediate Infusion-associated Reactions

Severity	Symptoms (such as, but not restricted to)	Management Guidelines
Mild reaction	Flushing Nausea Mild headache Tachycardia (pulse < 100 bpm) Abdominal pain	
REDUCE INFUSION RATE BY 50%
 
Contact investigator.
 
Give oral antihistamine/acetaminophen/paracetamol and/or IV antihistamine.
 
Prepare emergency equipment for any subsequent study treatment escalation.
 
Subject must be observed at site or medical facility for 2-4 hours after resolution of the symptoms.
 
Record all details of times, concomitant medications, and infusion rates.
 
Draw IgE and total GAA sample 6 to 8 and 24 hours after the start of the infusion reaction (2 samples).
 
IF SYMPTOMS PERSIST:
 
STOP THE INFUSION
 
After 30 minutes, if subject has improved, increase to previous infusion rate on direction of investigator/designee.
 
If subject has not improved after 60 minutes, consult with investigator as to whether additional medications should be administered.
 
If subject reacts for second time after return to the prior infusion rate, reduce rate by 50% and contact investigator/designee.
 
IF IN DOUBT, STOP INFUSION

Table 19: Guidelines for Management of Immediate Infusion-associated Reactions (Continued)

Severity	Symptoms (such as, but not restricted to)	Management Guidelines

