Severe reaction, anaphylaxis, or anaphylactoid reactions	Chest pain Generalized urticarial/angioedema Symptomatic hypotension(subject feeling faint, paleness) Hoarseness of voice/laryngeal edema Bronchospasm	** STOP INFUSION ** Activate emergency response and immediately contact investigator. For chest pain and symptomatic hypotension, initiate emergency procedures. Administer high-flow oxygen or intubate and mechanically ventilate as appropriate. Give IM adrenaline 300 mcg EpiPen into thigh (avoid buttock). If no response, repeat dose in 5 minutes. Prepare infusion of adrenaline 3 mg/50 mL NS (60 µg/mL), if needed. Give IV fluids 10- to 20-mL/kg fluid bolus on direction of PI/designee. Give IV antihistamines (promethazine 25 to 50 mg in 10 mL WFI over 2 to 3 minutes). Give IV steroids (hydrocortisone 100- to 500-mg bolus IV injection; dilute in 10 mL NS for doses between 100 and 500 mg) and infuse over 2 minutes. Give nebulized beta-2 agonists with high-flow oxygen on direction of PI/designee. Administer other treatments and/or transfer patient to hospital/ ICU as recommended by investigator/ designee. Observe subject for a minimum of 24 hours after resolution of the event. If deemed appropriate by PI/investigator, study treatment infusion can be re-initiated 7 to 14 days with premedications and at the 4-hour duration. Draw IgE and total GAA sample 6 to 8 and 24 hours after the start of the infusion reaction (2 samples). Report SAE if criteria for SAE reporting are met.

Abbreviations: GAA = human acid α -glucosidase; IgE = immunoglobulin E; IM = intramuscular; IV = intravenous; NS = normal saline; PI = Principal Investigator; SAE = serious adverse event; WFI = water for injection

Sources: Vogel 2010; Sampson et al 2006

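### Table 19 allows infusion to restart 7 to 14 days after anaphylaxis, although Section 8.5 requires withdrawal; Section 10.6 also gives two different waiting times for home infusion

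*Protocol*

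**What the plan says.** Section 8.5 has two lists. Under the first, subjects may be discontinued. Under the second, the wording is compulsory: "Subjects must discontinue study medication and be withdrawn from the study if they meet any of the following stopping criteria". The first item on that second list is "Anaphylactic reaction to study treatment, as defined by the Sampson Criteria", with the criteria in Appendix 1.

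Section 11.1.3 introduces Table 19 and says that it "also provides a guideline for management of IARs and anaphylaxis". It refers the reader to Appendix 1, and leaves it to the investigator's "discretion to follow the guidelines or implement treatment protocol that their center is accustomed to following". The most serious row of the table is headed "Severe reaction, anaphylaxis, or anaphylactoid reactions". After the emergency measures and the observation period, that row says: "If deemed appropriate by PI/investigator, study treatment infusion can be re-initiated 7 to 14 days with premedications and at the 4-hour duration".

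On home infusion, the opening text of Section 10.6 requires prior treatment "for a period of at least 6 months and not having experienced an IAR" in the preceding 6 months. The inclusion list in the same section requires: "Received ATB200/AT2221 treatment for a minimum of one year". The synopsis gives 6 months.

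**The concern.** The investigator turns to Table 19 during and just after a reaction. Its anaphylaxis row offers a restart that a compulsory stopping rule in another section forbids, and nothing in the row sends the reader to that rule. Section 11.1.3 points only to Appendix 1, which gives diagnostic criteria and no instruction on withdrawal.

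What is at stake is subject safety. The introduction (Section 6.1) records life-threatening anaphylactic reactions with the existing enzyme replacement therapy, so the hazard is foreseeable. There is also a reporting consequence. Re-dosing after Sampson-defined anaphylaxis would follow Table 19 and breach Section 8.5, so it would be unclear how to classify the deviation. The final report will summarise important deviations (SAP Section 7.3) and analyse anaphylactic reactions (SAP Section 10.3.3.3).

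The two home-infusion durations are a smaller matter: sites could apply different eligibility rules to subjects in the same position.

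**Working it through.** The main point needs no calculation. It rests on setting the texts side by side.

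| Question | Section 8.5 | Table 19, most serious row |
|---|---|---|
| Does it cover anaphylaxis? | Yes, Sampson-defined | Yes, named in the row heading |
| Action on study drug | Discontinue and withdraw | Restart possible at 7 to 14 days |
| Force | Compulsory | Investigator's judgement |
| Refers to the other? | No | No |

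1. **Can a reaction in this row meet the Sampson criteria?** Yes. The row lists generalised urticaria or angioedema and bronchospasm. Appendix 1, criterion 1, is met by acute skin or mucosal involvement together with respiratory compromise. A subject with both of those listed symptoms, of acute onset, therefore falls under the Section 8.5 rule.

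2. **Does the row separate such cases from the rest?** No. Section 11.1.3 defines five severity grades and gives systemic anaphylactic reaction as its example of a life-threatening one. Table 19 has only three rows (mild, moderate, and the combined severe row). Severe and life-threatening reactions therefore share one row and one restart line.

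3. **Does nearby text resolve the conflict?** No. Two other places are compatible with dosing after anaphylaxis. Section 10.2.12 asks for a third IgE sample just before the next dose following anaphylaxis or a moderate to severe reaction. The Section 10.6 exclusion list bars from home infusion anyone with anaphylaxis at any time, a step that would be largely redundant if every such subject had been withdrawn. Neither grants permission to re-dose, but neither points to Section 8.5.

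4. **Frequency.** The documents report no count of Sampson-defined anaphylaxis and no count of re-dosing after it, so none is estimated.

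5. **Home-infusion duration.** The Section 10.6 opening text and the synopsis say 6 months; the Section 10.6 inclusion list says one year. The Amendment 8 entry in the summary of changes records a move from 12 to 6 months, which identifies 6 months as the intended value. Largest extra wait if the one-year criterion is applied: 12 − 6 = 6 months per subject.

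6. **Severe-reaction exclusion for home infusion.** The Section 10.6 opening text excludes any history of a severe infusion-associated reaction. The synopsis and the Section 10.6 exclusion list refer to recurrent severe or life-threatening reactions. A subject with one severe, non-life-threatening reaction more than 6 months earlier is barred by the Section 10.6 opening text but not by the synopsis or the exclusion list.

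**The case against.** The strongest reply is that a permissive line in a table of guidelines cannot override a compulsory rule. Section 11.1.3 makes the table discretionary and sends the reader to the same Sampson definition that Section 8.5 uses. The row covers three kinds of reaction, and the restart line is proper for those that do not meet the criteria.

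Other safeguards would usually act within the 7 to 14 days. A life-threatening reaction is a serious adverse event and must reach the sponsor within 24 hours (Sections 11.1.2 and 11.4.1). The Safety Steering Committee can meet ad hoc (synopsis and Section 8.2), and the Medical Monitor and the committee can stop treatment (Section 8.2). Section 15.3 does not permit dosing deviations that could significantly affect safety. The IgE instruction also covers moderate and severe reactions that may properly be followed by further doses, so it is weak evidence of intended re-dosing after anaphylaxis.

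On home infusion, the longer period is the cautious one, and each request is decided case by case with prior ethics and regulatory approval. Finally, the study is closing, and no other protocol was available to show whether this text is reused.

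All of this stands, and it keeps the risk low. It does not remove the conflict. The safeguards depend on someone recognising that Section 8.5 applies, and the table meant for managing anaphylaxis does not say so.

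**Conclusion.** The concern holds. The Table 19 row that names anaphylaxis lacks an exception for Sampson-defined cases, and as written it offers an option that Section 8.5 forbids. It should be corrected because it is a safety instruction and the correction is short. The likelihood of harm is judged low, on the reading that the compulsory rule prevails over a discretionary table and that the serious-event reporting chain works as described. No frequency can be given, and no estimate, interval or planned analysis changes.

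The home-infusion duration is a genuine but minor inconsistency: at most 6 months' extra delay per subject, in the cautious direction. The severe-reaction wording also differs between places, and the documents do not show which version the sponsor intends.

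The SAP introduction expects database lock on 24 July 2024, with subjects moving to commercial product or, for a few, to an expanded access study. The practical value now lies mainly in any continuing protocol that carries the same text; whether one does cannot be checked from these documents.

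**What to change.** - **Table 19, most serious row.** Make the restart line conditional. If the reaction does not meet the Appendix 1 (Sampson) criteria, the investigator may restart 7 to 14 days later, with premedication and over 4 hours. If it does meet them, stop study drug and withdraw the subject under Section 8.5.
- **Section 10.6, inclusion list.** Replace one year with 6 months, to agree with the opening text and the synopsis.
- **Severe-reaction exclusion for home infusion.** Choose one wording and use it in the synopsis, the Section 10.6 text and its exclusion list. This is a clinical choice for the sponsor; until it is made, applying the stricter wording (any past severe reaction) is the safe course.

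The cost is one table line, one criterion and one harmonised exclusion, with no new data and no analysis work. In this study the change would need a formal amendment with ethics and, where required, regulatory approval (Section 15.3). With close-out under way, it is more sensible to make the edits in any continuing protocol that reuses the text.

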11.2. Relationship to Study Treatment

The investigator or a medically qualified sub-investigator will review each event and assess its relationship to study treatment based on available information according to the following guidelines:

- **Definite:** A reaction that follows a distinct temporal relationship from administration of study treatment; that follows a known reaction to the agent or chemical group of

the study treatments; and that cannot be explained by the subject's clinical state or other factors.

- **Probable:** A reaction that follows a reasonable temporal sequence from administration of study treatment; that follows a known or expected response pattern to the suspected study treatment; and that could not be reasonably explained by the known characteristics of that subject/subject's clinical state.
- **Possible:** A reaction that follows a reasonable temporal sequence from administration of study treatment; that follows a known or expected response pattern to the suspected study treatment; but that could readily have been produced by a number of other factors.
- **Unlikely:** A reaction that does not follow a reasonable temporal sequence from administration of study treatment. However, causality from study treatment cannot be ruled out.
- **Unrelated:** A reaction for which sufficient data exist to indicate that the etiology is unrelated to study treatment.

For the purpose of reporting SAEs to regulatory authorities and IRBs/ECs, any AE assessed by the investigator as definitely, probably, or possibly related to ATB200 and/or AT2221 will be considered "related" to study treatment (ie, associated with the use of study treatment). Any AE assessed as unlikely or unrelated will be considered "not related" to study treatment (ie, not associated with the use of study treatment).

11.3. Assessment of Intensity

The following definitions for rating intensity will be used for all AEs:

- **Mild:** Awareness of sign, symptom, or event, but the AE is easily tolerated and does not interfere with daily activity.
- **Moderate:** Discomfort enough to cause interference with usual activity and may warrant intervention, but the subject is still able to function.
- **Severe:** Incapacitating with inability to do usual activities or significantly affects clinical status, and requires medical intervention.

When the determination of AE intensity rests on medical judgment, the determination of intensity must be made with the appropriate involvement of the investigator or a medically qualified sub-investigator.

It is important to distinguish the difference between SAEs and events that are deemed as severe in intensity. Adverse events of severe intensity are not serious if one of the definitions in Section 11.1.2 is not met; AEs of any intensity must be reported as SAEs if one of the definitions in Section 11.1.2 is met.

11.4. Reporting Adverse Events

Information regarding AEs is to be obtained by questioning or examining subjects.

At each visit, beginning from the time written informed consent is provided until 30 days after the last treatment visit, all new complaints and symptoms (ie, those not existing before subjects provide informed consent) must be recorded as AEs in the eCRF and in subjects' source records. Findings documented on Screening ECGs that are unknown to subjects (ie, asymptomatic subjects) should be recorded as medical history (inclusive of FVC and 6MWT, plasma CK, ALT, AST, and urine Hex4 lab results).

- Pre-existing complaints or symptoms that worsen (eg, increase in intensity, frequency) after subjects provide informed consent must be entered in the AE eCRF module.
- CS laboratory abnormalities must be reported by the investigator as an AE or SAE as appropriate.
- CS changes to Screening ECG results must be reported by the investigator as an AE or SAE as appropriate. CS values will be provided in [Appendix 2](#).
- AEs related to a protocol-required procedure.

For each reported AE, the date the event started and ended, action taken, outcome (resolved, resolved with sequelae, ongoing, or fatal), intensity, and relationship to study treatment must be noted. Every effort should be made to report the start and end time AEs occurred.

All subjects who have AEs, whether or not events are considered associated with the use of ATB200 administered as a single agent or the use of ATB200 co-administered with AT2221, must be monitored to determine the outcome. The clinical course of AEs will be followed according to accepted standards of medical practice, even after the end of the study, until their health has returned to baseline status or stabilized or have otherwise been explained. Should an AE result in death, a full autopsy report should be supplied, if possible. For all AEs that require or result in subject discontinuation from the study, relevant clinical assessments and laboratory tests will be repeated as clinically appropriate, until final resolution or stabilization of the event(s).

11.4.1. Reporting Serious Adverse Events

If an AE is serious (as defined in Section [11.1.2](#)), the investigator must submit a SAE report form at the time the SAE is identified. All SAEs must be immediately reported by the investigator to Amicus or Amicus' representative, but no later than 24 hours after any study site personnel is aware of the event. Serious adverse event report forms must be faxed to the designated Safety Fax number ([contact]). All supporting documentation available at the time of reporting, with all subject identifiers redacted in accordance with local requirements, must be included in the fax along with the SAE report form. FAX reporting is preferred, but in case of no access to a fax machine, send documentation to the following email address: [contact].

The initial report must be as complete as possible. All known details of the SAE, and an assessment of the causal relationship between the event and ATB200 administered as a single agent, the use of ATB200 co-administered with AT2221, or study procedure should be included in the initial report. All information not available at the time of the initial report (eg, event end date, discharge summary, results of diagnostic procedures/evaluations related to the event, etc)

must be provided in a follow-up report. Follow-up information must be reported using the designated fax number within 24 hours of receipt at study sites.

Every attempt should be made to describe events in terms of a diagnosis. If a clear diagnosis has been made, individual signs and symptoms should not be recorded unless they represent atypical or extreme manifestations of the diagnosis, in which case they should be reported as separate events. If a clear diagnosis cannot be established, each sign and symptom must be recorded individually.

Study endpoints that meet SAE criteria (as per Section 11.1.2) must also be immediately reported by the investigator to Amicus or Amicus' representative but no later than 24 hours after any study site personnel is aware of the event.

If a nonserious event becomes serious, the event must be reported as described above.

If the investigator becomes aware of an SAE in a subject or receives an unsolicited report of an SAE from a subject more than 30 days after the last treatment, and considers the event possibly, probably, or definitely related to previous study treatment, she/he should contact the Amicus Medical Monitor to determine how the SAE should be documented and reported.

The Amicus Medical Monitor will determine the expectedness of AEs according to current safety reference document (eg, current investigator brochure or other safety-related information as available).

